
RATIONALE

The rationale for the proposed trial is summarized below:

1. **More than two-third** of SCD children followed up at Sainte-Justine UHC are either vitamin D deficient or insufficient during summer and fall and may therefore clinically benefit from improving their vitamin D status.
2. Given the low dietary and supplemental intakes of vitamin D of SCD children, their poor compliance to vitamin D supplementation, their compromised cutaneous synthesis of vitamin D, the presence of other potential contributing factors (e.g. impaired vitamin D metabolism, increased

nutritional demands, lactose intolerance) and the poor adherence to the CanHaem clinical practice guidelines¹⁴ regarding vitamin D, a vitamin D nutritional intervention is clinically and ethically desirable.

3. The fact that conditions associated with vitamin D deficiency/insufficiency are similar to SCD-related complications suggests that correcting vitamin D nutrition of these children may potentially result in clinical improvements and ultimately a better quality of life.

4. Very few SCD children in our cohort had serum 25OHD levels > 75 nmol/L (i.e. 6%), the suggested target level for the extra-skeletal effects of vitamin D. Given that some clinical benefits have been demonstrated in SCD children when serum 25OHD exceeds 75 nmol/L, an effective intervention strategy aimed at normalizing vitamin D status while ensuring reasonable compliance is warranted.

HYPOTHESIS

We hypothesize that administration of a single oral bolus of 300,000 IU of vitamin D₃ to children with SCD represents a safe, acceptable and clinically feasible regimen that will result in the attainment of vitamin D sufficiency (25OHD levels >75 nmol/L) in 80% of participants and in mild improvements in some clinical outcome measures after 3 months.

RESEARCH OBJECTIVES

Primary objectives:

- To assess the feasibility of recruitment and intervention (vitamin D₃ bolus)
- To assess the acceptability of the intervention by patients and parents
- To assess the safety of the vitamin D₃ bolus (serum and urinary calcium levels, serum 25OHD)

Secondary objectives:

- To observe the mean change in total serum 25OHD from baseline to 3 months. At 3 months, a raise of the 25OHD level to 75nmol/L or more is expected.

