Randomisation and allocation concealment: Using a computer-generated random list, children will be randomly allocated to placebo or intervention, using random permuted blocks. The Applied Clinical Research Unit of Sainte-Justine UHC will generate the randomisation scheme. Group allocation codes will be held in a secure location with a restricted access by the Central pharmacy (Sainte-Justine UHC). All participants and research personnel, including the nurse, research trainee and research team will be blinded to group assignment.

Interventions: Experimental group: a single liquid bolus of 300,000 IU oral vitamin D₃, which corresponds roughly to 3,333 IU/day; Control group: placebo identical in taste and appearance. The proposed dose of bolus vitamin D₃ is based upon a previous report showing that 4,000 to 7,000 IU/day administered to SCD children over 12 weeks was effective to correct vitamin D insufficiency in more than 95% of their cohort and led to some clinical improvements¹¹.

Co-interventions: In addition, all subjects will be provided with a 3-month prescription of vitamin D₃ tablets (1,000 IU/tablet) to comply with the CanHaem guidelines¹⁴ and instructed to take 1 pill per day. The research trainee will assess calcium intake and if deemed too low, participants will also receive a prescription for calcium supplements in order to ensure adequate daily calcium intake. The reason for such a co-intervention is to prevent symptoms of hypocalcemia in those who take supplemental vitamin D but have a low calcium intake.

Overall, participants in the experimental group will be taking 4,333 IU/day + dietary vitamin D intake, which falls within the range of 4000 to 7000 IU/day previously found to correct suboptimal status of SCD children¹¹. Placebo group will be taking 1,000IU/day in addition to dietary vitamin D intake. Previously, the evaluation of dietary vitamin D intakes of a sample of children attending the SCD clinic at UHC Sainte-Justine (n = 46) revealed that the children took, on average, 292 +/- 128 IU of vitamin D per day². Therefore, by taking into account dietary vitamin D intakes similar to what we have previously found, the participants in the experimental group will take 4, 625 IU of vitamin D per day in total (supplement + dietary intakes) while participants in the placebo group will take 1, 292 IU per day.

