participation; iv) response rates to questionnaires and compliance to the interventions will be gathered throughout the trial by the research trainee.

2. *Safety*: Urine will be collected by the research nurse at baseline and 3 months and calcium/creatinine ratio measured using automated methods (Clinical Biochemistry Service, Sainte-Justine). At baseline, participants will be provided with a container to collect urine on day 7 (\pm 3days) post-bolus along with the team endocrinologist's prescription for the assessment of urine calcium and creatinine. They will be instructed to bring the urine to the nearest medical clinic for measurement. Results will be communicated to the team endocrinologist for evaluation and management. Serum calcium will be measured if deemed necessary by the endocrinologist. Code breaking will be done only if required for patient management. The proportion of children with episodes of hypercalciuria, hypercalcemia or serum 25OHD levels $>$ 250nmol/L as well as any other adverse health effects will be documented at endpoint while weekly follow-up phone calls will be made by the research trainee to inquire about adverse events.

3. *Dietary intakes and sun exposure*: The research trainee will assess calcium and vitamin D intakes at baseline and endpoint by means of a validated food frequency questionnaire¹⁵. Analysis of the FFQ will be based on values from the Canadian Nutrient File version 2010 and the US Department of Agriculture National Nutrient Database for Standard Reference as done previously¹⁶. Sun exposure will be evaluated with a non-validated questionnaire at both timepoints.

4. *Mean change of 25OHD levels*: To measure this outcome, blood will be collected at baseline and 3 months post bolus by the research nurse. Serum 25OHD will be measured in batches by tandem mass spectrometry at the Clinical Biochemistry Service of Sainte-Justine UHC.

5. *Clinical outcomes*:

Those outcomes will be either collected or measured at baseline and endpoint:

- (i) Growth: weight, height and BMI will be retrieved from medical records.
- (ii) Haematological: complete blood count, lactate dehydrogenase (as index of hemolysis), bilirubin and creatinine. These assessments are routinely performed in these children and will be extracted from medical records.
- (iii) Inflammatory: serum TNF and IL-6 will be measured by ELISA kits in [name] lab.

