Feasibility: Preliminary data showed that we already have access to a large cohort of patients (n=307) through our ongoing collaboration with two SCD expert haematologists. Infrastructure is already in place since we have previously performed data collection in more than a third of the SCD population (n=116) followed up at the clinic. Study is not invasive as those children have their blood drawn at each follow-up visits. Although a certain level of involvement is required from participants and their parents, we believe that a nutritional intervention will be perceived as more acceptable than a pharmacological treatment. For all these reasons, we anticipate few recruitment issues. Supplements (both boluses (placebo and vitamin D₃) will be provided by Euro-pharm at no cost for the study. Ethics approval will be sought and a no-objection letter will be requested from Health Canada, pending results of this review. The no-objection letter is required given that the proposed total amount of vitamin D₃ exceeds the upper intake level (UL) of vitamin D recommended for otherwise healthy children aged 4-8 years (i.e. 3,000 IU) and 9 and older (i.e. 4,000 IU).

[figure not shown]

Fig.1 Experimental design

STATISTICAL ANALYSIS

The analyses will be made using the intention-to-treat model where all subjects are included regardless of their adherence to the study protocol. Differences in outcomes between experimental groups at baseline and endpoint will be assessed using parametric Student's t test or non-parametric

Mann Whitney U test for continuous variables and Chi-square test or Fisher's exact test for categorical variables. Intragroup differences will be assessed using paired Student's t test with Bonferroni adjustment. Analyses will be performed under allocation concealment with unblinding occurring after trial completion and analysis of primary outcomes. Given the pilot nature of our study, subanalyses will be undertaken on variables that may potentially influence the response to vitamin D such as genotype, season of the year or baseline vitamin D status. However, these analyses remain exploratory.

CLINICAL SIGNIFICANCE

By implementing this pragmatic and highly acceptable intervention and achieving a compliance of 100% with the administration of the vitamin D bolus, we expect to: 1) correct vitamin D insufficiency in SCD children; 2) avoid monitoring their 25OHD levels on a regular basis; and 3) ultimately demonstrate improvements in clinical outcomes.

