baseline 25OHD levels to be minimal for the following reasons. First, a very small proportion of our cohort (i.e. 6%) had normal 25OHD levels (>75 nmol/L)². Second, vitamin D toxicity is associated with high chronic intake and serum 25OHD levels > 250 nmol/L¹⁹. However, using a more conservative approach, the report on Dietary reference intakes (DRI) for calcium and vitamin D stated that 25OHD levels above 125 nmol/L may be associated with risks²⁰. In our cohort, none displayed serum 25OHD considered toxic whereby the maximum 25OHD concentration achieved was 99 nmol/L, which is well below toxic levels². Furthermore, the majority of blood draw were made in spring and in summer, 2 seasons in which we expect 25OHD serum levels to be higher due to sun exposure. Third, vitamin D bolus administration has not been associated with reports of toxicity in both non-SCD children (bolus of 300,000 and 600,000 IU)²¹ and SCD patients (bolus of 240,000 IU)⁹. Thus, most of our participants are vitamin D deficient or insufficient and will likely benefit from raising their 25OHD levels. Finally, given that the study includes only one vitamin D bolus and lasts only 3 months, the risk of toxicity for the patients is minimal.

Use of a placebo: The use of a placebo in this study is justified by the fact that both groups (experimental and placebo) will received, in addition to the study intervention, a prescription for a supplementation of vitamin D₃ of 1,000 IU per day, which corresponds to the current guidelines. Therefore, the children in the placebo group will not be exposed to higher risks of vitamin D deficiency. The difference of vitamin D received by experimental group (4, 625 IU) and the placebo group (1, 292 IU) should allow us to discriminate enough the effect of the intervention compared to the placebo.

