No pre-selection of children based on their baseline vitamin D status or season: All eligible SCD children will be asked to participate in this study regardless of their baseline vitamin D status or season of the year. The absence of pre-screening is justified by our preliminary data, which showed that a large proportion of SCD children are either vitamin D deficient or insufficient during summertime (insufficiency 33% and deficiency 66%)². Moreover, serum 25OHD levels of these children declined seasonally (45.6 ± 19.5 nmol/L in summer vs. 33.9 ± 15.9 nmol/L in fall, $p=0.01$). From these observations, we anticipate that nearly all SCD children would benefit from such an intervention. Although it is suggested that serum 25OHD > 75 nmol/L is likely associated with extra-skeletal benefits, the optimal target serum 25OHD is still unknown. Hence, by restricting the intervention to children with baseline vitamin D deficiency/insufficiency, we would exclude children that may benefit. The absence of pre-selection will also allow us to study the impact of the baseline status on the efficacy of the intervention in addition to facilitate the implementation of the intervention in clinic.

TEAM INFORMATION

Principal investigator:

[name], RD

Associate professor, Department of Nutrition, Université de Montreal Researcher, CHU Sainte-Justine Research Center

Areas of expertise: vitamin D, calcium, bone health, inflammation, rare diseases, chronic diseases

Roles: The PI is a PhD registered dietitian with specific training in vitamin D whereby she has accumulated more than two decades of experience. The PI will oversee study logistics along with her research trainee, supervise data collection, and lead the data analysis, manuscript writing, team meetings and knowledge dissemination. Her lab personnel will process the blood samples and perform measurements using ELISA kits.

[name]

Endocrinology Division

Department of pediatrics

CHU Sainte-Justine

Researcher, CHU Sainte-Justine Research Centre

Areas of expertise: vitamin D, bone health, metabolic bone diseases

Roles: [name] is a pediatric endocrinologist and the director of the Pediatric Bone Health Unit at the CHU Sainte-Justine. She will prescribe the daily vitamin D and calcium supplements and oversee all safety aspects of the intervention. She has collaborated to the design of the research protocol and will be involved in data analysis and interpretation, manuscript editing, and knowledge dissemination.

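### Change is tested only within each arm, and arms are compared only by unadjusted tests at each visit; a baseline-adjusted between-arm comparison should replace both.

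*Protocol*

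**What the plan says.** The Statistical Analysis section of the protocol fixes two kinds of test for continuous outcomes.

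- **Between arms:** "Differences in outcomes between experimental groups at baseline and endpoint will be assessed using parametric Student's t test", with Mann-Whitney U as the non-parametric alternative (chi-square or Fisher's exact test for categorical variables).
- **Change:** "Intragroup differences will be assessed using paired Student's t test with Bonferroni adjustment".

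No baseline covariate is named. Baseline vitamin D status and season appear only as factors in subanalyses that the section itself calls exploratory.

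Other sections treat change as a target. The first secondary objective is "To observe the mean change in total serum 25OHD from baseline to 3 months", and item 4 of the Outcomes is headed "Mean change of 25OHD levels". For growth, haematology, inflammation, bone health, pain, complications and quality of life, item 5 says: "Those outcomes will be either collected or measured at baseline and endpoint". Under Ethical Issues, the paragraph on use of a placebo says that the intake difference between arms "should allow us to discriminate enough the effect of the intervention compared to the placebo".

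**The concern.** The only analysis of change that is stated does not use the control arm. A change within the bolus arm cannot be credited to the bolus, for two reasons found in the protocol.

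- Both arms are prescribed a daily supplement. On the control arm, the Co-interventions paragraph says: "Placebo group will be taking 1,000IU/day in addition to dietary vitamin D intake". The placebo arm may therefore change as well.
- Season moves the marker. The paragraph on not pre-selecting children reports that "serum 25OHD levels of these children declined seasonally", from 45.6 to 33.9 nmol/L. Recruitment and data collection run from May to March.

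The between-arm endpoint test does use the control arm, but it ignores a baseline value that is measured anyway. Testing the arms against each other at baseline tells the reader nothing useful, because allocation is random and any difference is due to chance.

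The trial is meant to inform a larger RCT. For outcomes measured twice, the useful product is an estimated bolus effect against placebo with its precision. Two separate within-arm p-values do not supply that.

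**Working it through.** The protocol gives no power or precision figure for change. Its sample size concerns the proportion reaching 75 nmol/L, so there is no plan figure to reproduce on this point.

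**Inputs from the protocol:** 30 evaluable children per arm; two-sided alpha 0.05; 25OHD SDs from 15.9 to 20.4 nmol/L; summer and fall means 45.6 and 33.9; target of 80% at or above 75 nmol/L.

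**Inputs assumed:** the baseline-to-endpoint correlation r, a clinical effect of 0.5 SD, a placebo 25OHD mean of 60 to 70 nmol/L, and normality.

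**1. Precision of the arm comparison.** Relative to the endpoint-only test, ANCOVA multiplies the variance by 1 − r². The equivalent gain in patients is 1/(1 − r²). The noncentrality is 0.5 × √(30/2) = 1.936 for the endpoint test (58 df) and 1.936/√(1 − r²) for ANCOVA (57 df).

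| r (assumed) | 1 − r² | Equivalent sample | Power, endpoint t | Power, ANCOVA |
|---|---|---|---|---|
| 0.3 | 0.91 | 1.10 | 0.48 | 0.51 |
| 0.5 | 0.75 | 1.33 | 0.48 | 0.59 |
| 0.7 | 0.51 | 1.96 | 0.48 | 0.76 |
| 0.9 | 0.19 | 5.26 | 0.48 | 0.99 |

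Simulation agrees to within 0.01, and with no true effect the type I error was 0.046 to 0.052. A plain between-arm test of change scores has variance factor 2(1 − r), which is 1.40 at r = 0.3, so it is worse than the endpoint test when r is below 0.5. That is why ANCOVA is preferred to a test of change scores.

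**2. 25OHD itself.** If 80% of the bolus arm reach 75 nmol/L, the arm mean is 75 + 0.842 × SD: 88.4 at SD 15.9 and 92.2 at SD 20.4. Against a placebo mean of 60 or 70:

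- SD 15.9: (88.4 − 60)/15.9 = 1.79, or (88.4 − 70)/15.9 = 1.16.
- SD 20.4: (92.2 − 60)/20.4 = 1.58, or (92.2 − 70)/20.4 = 1.09.

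The lowest power of the unadjusted t test over these cases is 0.985.

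**3. What within-arm tests show when there is no bolus effect.** Let both arms truly change by the same amount d, in SDs of the change, and let p be the power of the paired t test at n = 30. Exactly one arm is significant with probability 2p(1 − p).

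| d (assumed) | p at 0.05 | One arm only, alpha 0.05 | Bonferroni over 2 | Bonferroni over 10 |
|---|---|---|---|---|
| 0.3 | 0.355 | 46% | 38% | 18% |
| 0.4 | 0.563 | 49% | 49% | 35% |
| 0.5 | 0.754 | 37% | 46% | 48% |

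Half of each figure is the misleading direction, bolus arm only. At alpha 0.05 that is about 19% to 25%. The number of tests covered by the adjustment is not stated, so 2 and 10 are illustrations; neither removes the problem.

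**4. Season.** The seasonal gap is 45.6 − 33.9 = 11.7 nmol/L. If every child's follow-up spanned it, the standardised change would be 11.7/(SD × √(2(1 − r))). With SD 15.9 to 19.5 and r 0.3 to 0.7 this runs from 0.51 to 0.95, and a single-arm paired test would be significant in 77% to over 99% of trials without any bolus effect. This is an upper case, because visits will be spread over seasons.

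**The case against.** The strongest reply is that the bolus effect is already estimated. Under randomisation the baseline means are equal in expectation, so the endpoint difference and the difference in change have the same expected value. The placebo contrast is thus used, at endpoint. This stands: the planned comparison is valid, and what remains is lost precision, exposure to chance baseline imbalance, and the mismatch with an objective worded as change.

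Second, the protocol never says that it will infer an effect because one arm is significant and the other is not. This also stands. The percentages in step 3 illustrate why within-arm tests are uninformative; the recommendation does not depend on them.

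Third, because mean change is listed as an outcome, the between-arm sentence might be read to cover it. This fails on the wording: the comparison is set at baseline and at endpoint, and change does not exist at baseline. If it was intended, it should be said.

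Fourth, covariates are often left to an SAP, these are secondary outcomes of a pilot with objectives worded as observation, and the protocol concedes that 3 months is short for clinical benefit. The pilot status limits the weight of the point. But the protocol names its tests itself, so this is a stated choice rather than a detail left open. The gain is small at low r (0.48 to 0.51 at r = 0.3) and large only where the endpoint depends strongly on the baseline.

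**Conclusion.** The concern holds. For continuous outcomes the protocol states no between-arm comparison of change or of the endpoint given baseline, although change is an objective and both values are collected. The planned endpoint test is unbiased.

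The cost is a variance 1/(1 − r²) times that of ANCOVA: 1.10 to 5.26 times for r from 0.3 to 0.9. All values of r and the 0.5 SD effect are assumptions. The loss is immaterial for 25OHD if the 80% target is met and the placebo mean is 60 to 70 nmol/L. It is material for the milder clinical effects that the protocol hypothesises, and greatest for height and weight in children aged 5 to 17, whose 3-month values depend strongly on their starting values. The feasibility, acceptability and adverse-event outcomes are untouched. The change should be made, but the trial does not stand or fall on it.

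**What to change.** In the Statistical Analysis section, replace the between-arm and within-arm sentences for continuous outcomes with:

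> For continuous outcomes measured at both visits, 3-month values will be compared between arms by ANCOVA with arm and the baseline value of the outcome (for 25OHD also season of the baseline visit), reporting the adjusted difference with 95% CI. A log-transformed or rank-based version will be used if residuals are clearly non-normal. Within-arm changes will be reported descriptively as means with 95% CIs.

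The choice between the original, log and rank versions should be settled on blinded data, so that it cannot follow the result.

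Delete the between-arm significance tests at baseline. Keep the chi-square or Fisher comparison for categorical outcomes, and leave the feasibility, acceptability and adverse-event reporting as it is.

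The cost is wording only. Baseline values and visit dates are already collected. The model uses one degree of freedom for the baseline value and, for 25OHD, one to three for season.

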We plan to carry out this project over a 2-year period. Timeline will be divided into three major segments:

- i) Ethics application and approval, and study set-up: October 2017-April 2018 (5 months)
- ii) Patient recruitment, data collection, sample processing and analysis: May 2018-March 2019 (11 months)
- iii) Data analysis, manuscript drafting and dissemination: March 2019-July 2019 (5 months)

BUDGET

This is a research project that is not subsidised. The vitamin D bolus and placebo will be provided at no cost by Euro-Pharm. The research trainee will be paid by two grants that she received (\$9,500 total + \$1,000 from her director) and by her part time job (2 days per week) as a dietician which will fill the difference for the minimum intake required for master's students. The other expenses will be covered by the research fund of the two principal investigators.

KNOWLEDGE TRANSLATION

Our key knowledge transfer goals are to increase knowledge and awareness to ultimately move research evidence into practice, improve patient's nutritional management and the role of dietitian in that respect, and inform future research priorities. The CanHaem existing guidelines are based on minimal data, collected in individuals of different ethnic backgrounds. Our study will thus provide additional evidence in a Canadian context that may prompt a change in clinical practice guidelines. To achieve the knowledge transfer goals, we will reach out to our target audiences via 1) presentations at international (e.g. American Society of Pediatric Hematology/Oncology (ASPHO)), national (e.g. Canadian Nutrition Society) and local conferences or to national/local groups and 2) peer and non-peer review publications in disciplines such as nutrition and hematology. Upon completion of the study, we will invite the study participants (parents and children) to a "Scientific Café" in order to present and discuss the results and gather their input and thoughts on the study and future participation. Finally, the study results will also be presented at the annual Symposium for Sickle cell disease, which is an event intended for SCD patients and their family.

REFERENCES

